5.3.3.7 Reactogenicity Events

Each patient will record local events, systemic events, and oral temperature in a diary daily for 7 days after each dose. Incidence of reactogenicity events will be analyzed by treatment arm and dose number.

The number of patients with injection site reactogenicity events and each of the solicited events (Redness, Swelling or hardening, Pain at injection site (without pressure), tenderness) as well as with systemic reactogenicity events and each of the solicited events (fatigue, fever, chills, headache, muscle aches, joint aches, nausea, vomiting, diarrhoea) will be shown.

Also, number of events will be estimated for grouped injection site reactogenicity events (Redness, Swelling or hardening, Pain at injection site (without pressure), tenderness) and grouped systemic reactogenicity events (fatigue, fever, chills, headache, muscle aches, joint aches, nausea, vomiting, diarrhoea). Each event will be counted once by day of registration in the patient's diary card (i.e.: if the same event is registered for 3 different days in the diary card of a specific dose, 3 events will be counted for that dose).

Summaries will be performed for All events and also according to the grade Mild, Moderate and Severe. The size of reaction for Redness and Swelling (or hardening) will be assigned with the measurement in cm, being Mild from 2.5 to 5, Moderate larger than 5 to 10 and Severe larger than 10. Patients may have self reported events under 2.5 cm as an event, but following formal guidance these will not be reported as reactogenicity event in the statistical analysis.

A listing of all events recorded in the diary card will be included.

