3.4. Safety Endpoints

- Incidence and severity of AEs, medically-attended AEs (MAEs), new-onset chronic illnesses (NCIs), and immune-mediated medical conditions (IMCs)
- Incidence and severity of local and systemic reactogenicity events
- Incidence and duration of hepatitis flares, defined as alanine aminotransferase (ALT) \geq 3 × upper limit of normal (ULN) and \geq 100 U/L
- Changes in ALT, aspartate aminotransferase (AST), alkaline phosphatase (AP), gamma glutamyl transferase (GGT), bilirubin total and direct, international normalized ratio (INR) and other laboratory parameters

Safety endpoints will be assessed separately for the 24-week Treatment Period and 52-week Follow-Up Period.

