7.1.1. Stopping Rules

In consultation with the DMC, the following Stopping Rules will be applied:

- ALT or AST $\geq 10 \times ULN$
- INR ≥ 1.3
- Total bilirubin $\geq 1.5 \times \text{ULN}$ (excluding patients with Gilbert Syndrome)
- Direct bilirubin $\geq 1.5 \times \text{ULN}$ (for patients with Gilbert Syndrome)
- SAEs
- Severe systemic reactogenicity event (see Appendix 1)

If any of the Stopping Rules are met in one or more patients in the sentinel cohort (ie, the first 12 patients dosed) and the event(s) is deemed possibly or probably related to study medication, dosing will be suspended pending DMC review. Similar procedures will be

applied if 2 or more patients in the sentinel or expanded study cohort together experience Stopping Rules deemed possibly or probably related to study medication at any time during the 24-week Treatment Period. DMC recommendations may include instituting modifications to ensure the safety of continued dosing or discontinuing the study.

If the study is halted based on a DMC decision or safety concern, the trial will only be restarted after notification of the competent authority via a substantial amendment.

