5.3 Summary of Statistical Methods

This study is designed as a phase 2 study, exploratory in nature, to evaluate the response to HepTcell in treatment-naïve patients with inactive CHB. Comparisons will be performed between HepTcell and Placebo at a two-sided type I error rate of 0.05 which will not be adjusted for multiple testing.

The study will be considered to have achieved proof-of-concept when the 2-sided p-value is <0.05. Accordingly, the primary and key secondary efficacy endpoints will present 2-sided 95% Confidence Intervals (95%Cls) when applicable.

Unless otherwise specified, efficacy analyses will be performed using the mITT population, where patients will be in the treatment arm to which they received. As described in more detail elsewhere, patients will be analysed according to the treatment of the most treatment received. Moreover, supportive efficacy analyses will be performed in the PP population. Safety related analyses will use the safety population, where patients will be analyzed according to the treatment that they receive.

All applicable baseline data will be summarized by treatment arm (HepTcell, placebo), unless specified otherwise. Safety and efficacy data will also be summarized by treatment arm and additionally by time-point of assessment and/or follow-up, when appropriate.

Continuous variables will be summarized using the number of observations (n), mean (95%CI, if appropriate), standard deviation (SD), Standard error (SE, if appropriate), median, first quartile (Q1), third quartile (Q3), minimum, and maximum along with the total number of patients contributing values.

Descriptive statistics for categorical/qualitative data will include frequency counts and percentages. The denominator for all percentages will be the total number of patients in the treatment arm and dose number (if applicable) within the population of interest, unless stated otherwise in the table footnote.

Change from baseline is calculated only for patients with non-missing values for both the baseline and the time-point of interest and will be missing otherwise.

Statistical comparisons will be performed between HepTcell and placebo at a 5% confidence level.

All relevant patient data will be included in listings. All patients entered into the database will be included in patient data listings. The listings will be generally sorted by treatment arm and then Patient ID, unless specified otherwise.

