5.3.16 Maintaining the Blind during the study

Patients will be unblinded **as necessary** to assess the relationship between the study medication and events that meet criteria for Stopping Rules. Patients who experience events that meet criteria for Stopping Rules will permanently terminate dosing.

If unblinding is required in the interest of the safety of a patient, an Investigator will discuss the matter with the Sponsor before unblinding. In a medical emergency, the Investigator or delegate may unblind via the IWRS for that patient without prior consultation with the Sponsor. In that event, the Investigator or delegate will notify the Sponsor as soon as possible that the randomization code has been broken for the patient. If the blind is broken, the date, time, and reason must be recorded.

Patients may also be unblinded for the processing of SAEs, expedited safety reports, and the emergency unblinding of patients, as detailed in a separate Safety Management Plan.

All statistical analysis will be performed by a blinded team of statisticians and statistical programmers, who will work in a secure area without any treatment identifying information. For the interim analysis the blinded team will handover all programs prepared using blinded information to the unblinded team who will then be able to prepare unblinded outputs required for the interim analysis as specified in Appendix 1.0 of this document.

No unblinded individual level data will be shared with anyone outside the unblinded team. The unblinded team will be defined in the Project Management Plan.

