14.3.4.1.3	Summary of Clinical Laboratory Hematology Results: Shift from baseline vs post-baseline category	Safety Population	Yes (Through D169)	
14.3.4.2.1	Summary of pre-dose Values and Change from baseline for Clinical Laboratory Biochemistry Results	Safety Population	Yes (Through D169)	
14.3.4.2.2	Summary of Abnormalities for Clinical Laboratory Biochemistry Results	Safety Population	Yes (Through D169)	
14.3.4.2.3	Summary of Clinical Laboratory Biochemistry Results: Shift from baseline vs post-baseline category	Safety Population	Yes (Through D169)	
14.3.4.3.1	Summary of pre-dose Values for Continuous Urinalysis Results	Safety Population	Yes	
14.3.4.3.2	Summary of Values for Categorical Urinalysis Results	Safety Population	Yes	

TFL Number	Title	Analysis Set	Included in	TOP LINE
			Final report	TABLES
14.3.4.3.3	Summary of Abnormalities for Clinical Laboratory	Safety Population	Yes	
	Urinalysis Results			
14.3.4.3.4	Summary of Clinical Laboratory Urinalysis Results:	Safety Population	Yes	
	Shift from baseline vs post-baseline category			
14.3.5 Reactoger	-			
14.3.5.1	Incidence of Reactogenicity Events	Safety Population	Yes	
14.3.6 Hepatitis F	Flares			
14.3.6.1	Incidence of Hepatitis Flares	Safety Population	Yes	
14.3.6.2	Summary of patients achieving HBsAg loss by Hepatitis Flares	Safety Population	Yes	
14.3.6.3	Logistic Regression Analysis for HBsAg loss by Hepatitis Flares at Day 169	Safety Population	Yes	
14.3.7 Vital Signs	5		,	I
14.3.7.1	Summary of Values and Change from baseline for Vital Signs: Results by Visit	Safety Population	Yes (Through D169)	
14.3.7.2	Summary of Values and Change from pre-dose for Vital Signs: Results after first and second dose	Safety Population	Yes (Through D169)	
14.3.7.3	Summary of Height, weight, and BMI change from baseline	Safety Population	Yes (Through D169)	
14.3.8 Electrocar	diogram Measurements (12-Lead ECG)			
14.3.8.1	Summary of Evaluation for 12-Lead ECG Results	Safety Population	Yes (Through D169)	
14.3.9 Physical E	xamination		,	
14.3.9.1.1	Complete Physical Examination after Baseline (Day 169/ET)	Safety Population	Yes	
14.3.9.1.2	Targeted and symptom-driven Physical Examination after Baseline	Safety Population	Yes (Through D169)	
Listing Number	Examination and Basonile			
16.2.1 Patient's D	Disposition			

22-Apr-2024

TFL Number	Title	Analysis Set	Included in	TOP LINE
			Final report	TABLES
16.2.1.1	Listing of Patient's Disposition and Status	All Patients in DB	Yes	

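### Reactogenicity is specified only dose by dose, with no after-any-dose count of patients and no worst grade per patient

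*SAP*

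**What the plan says.** Protocol 3.4 names the safety endpoint "Incidence and severity of local and systemic reactogenicity events". Diaries are kept for 7 days after each of six doses.

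SAP 5.3.3.7 sets the level of summary: "Incidence of reactogenicity events will be analyzed by treatment arm and dose number". It promises numbers of patients with any local event, any systemic event and each solicited event. On grade it says "Summaries will be performed for All events and also according to the grade Mild, Moderate and Severe"; here the word All refers to grades, not doses. On event counts it says "Each event will be counted once by day of registration in the patient's diary card".

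Under SAP 5.3, the default denominator for percentages is the "total number of patients in the treatment arm and dose number (if applicable) within the population of interest". SAP Appendix 1 lists one reactogenicity table, 14.3.5.1, titled "Incidence of Reactogenicity Events", in the Safety Population. The diary listing is 16.2.9.1.

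Protocol 7.1.1 makes a severe systemic reaction a Stopping Rule; severe local reactions are not on that list. SAP 5.3.16 and Protocol 6.4 give the consequence: "Patients who experience events that meet criteria for Stopping Rules will permanently terminate dosing".

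**The concern.** Safety is a secondary objective. A reader of the report will want to know what share of patients in each arm had a local or systemic reaction over the six-dose course, and how bad the worst one was. No specified output answers that.

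Three neighbouring outputs do not supply it:

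- **Adverse event tables.** Protocol 8.3.1 and SAP 4.3 keep non-serious solicited reactions out of the adverse events.
- **Event counts.** These are event-days, so three entries may be one patient on three days or three patients on one day each.
- **Grade rows.** No worst-grade rule is written, so a patient with a mild day and a moderate day could appear in both rows.

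The SAP does specify course-level summaries elsewhere: adverse events by maximum severity with each patient counted once (5.3.3.2), and patients with any hepatitis flare across treatment visits (5.3.3.8). Reactogenicity has no equivalent.

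The later-dose columns also describe a selected group, because a patient stopped at one dose is absent from every later denominator. Unlabelled, a falling rate could be read as improving tolerance.

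**Working it through.** **Plan figures.** The documents give no reactogenicity rate, so every rate below is an assumption. The inputs taken from the plan are six doses and 40 patients per arm. The sample size statement (3% versus 25%, two-sided 0.05, about 80% power) reproduces: at 40 per arm, power is 82.2% by the normal approximation and 78.0% by exact enumeration of Fisher's test. It serves here only to fix the arm size.

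**1. From a by-dose rate to the share of patients with any reaction.** Let the rate be a constant p at each of six doses, all six received.

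- Same patients each time: p
- Independent doses: 1 − (1 − p)^6
- Different patients each time: min(1, 6p)

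| Assumed p | Same patients | Independent | Different patients |
|---|---|---|---|
| 5% | 5% | 26.5% | 30% |
| 10% | 10% | 46.9% | 60% |
| 30% | 30% | 88.2% | 100% |

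For p = 10%, independence gives 1 − 0.9^6 = 1 − 0.531 = 0.469. In an arm of 40, six columns each showing 4 patients (10%) fit anything from 4 to 24 patients affected. Two arms with identical by-dose columns could differ by that much.

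**2. The exception.** If the stopping provision is followed, a patient can have a severe systemic reaction at only one dose. The by-dose patient counts for that category do not overlap, and their sum over the Dose 1 number is the share of patients. This does not work for mild, moderate, any-grade or local reactions, which can recur.

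**3. Conditional later-dose rates.** Suppose 10% of 40 patients are susceptible, with a 0.5 risk of a severe systemic reaction at each dose, and dosing ends at the first one.

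| Dose | Expected number dosed | Expected patients with event | Rate |
|---|---|---|---|
| 1 | 40 | 2.0 | 5.0% |
| 2 | 38 | 1.0 | 2.6% |
| 3 | 37 | 0.5 | 1.4% |
| 4 | 36.5 | 0.25 | 0.7% |
| 5 | 36.25 | 0.125 | 0.3% |
| 6 | 36.125 | 0.0625 | 0.2% |

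The events sum to 3.94, and 3.94/40 = 9.8% of patients. Other assumptions:

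- 10% susceptible, risk 0.3: 3.0% at Dose 1 falling to 0.55% at Dose 6; 8.8% of patients overall.
- 20% susceptible, risk 0.5: 10.0% falling to 0.4%; 19.7% overall.
- Everyone at the same risk of 2.5%: the rate stays at 2.5% at every dose; 1 − 0.975^6 = 14.1% overall.

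The fall therefore comes from differences in risk between patients. Stopping alone does not produce it.

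**The case against.** **The endpoint does not say per patient.** This stands. Counts of patients by arm, dose and grade are one legitimate estimate of incidence and severity, and the dose is a natural unit for a 7-day diary. Protocol 3.4 does frame the safety endpoints by period, including the 24-week Treatment Period. SAP 4.3 limits that split to endpoints also measured in follow-up, so the argument from period is supportive only.

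**A reader might infer that the endpoint will never be estimated.** The documents do not support that. The sentence promising numbers of patients does not itself repeat the restriction to dose, SAP 5.3.3 promises safety summaries by arm in general terms, there is no table shell, and the listing allows derivation. The supportable statement is that the course-level summary is not specified.

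**A reader might infer that any severe reaction removes a patient from later columns.** Under the Stopping Rules only a severe systemic one does. A stopped patient is still counted at the dose concerned and at all doses before it.

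**Attrition is visible elsewhere.** SAP 5.3.3.1 tabulates patients by dose number and SAP 5.2.1 gives reasons for early treatment discontinuation. That shows smaller groups, but not how many patients reacted.

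**The depletion example is hypothetical.** This also stands. Protocol 1.3 reports no effect of number of doses on safety parameters in Phase 1 and no severe injection site reactions, although that study gave three doses. From Dose 3 on, the expected count in the main example is half a patient or less.

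**The table is descriptive, in a trial that the SAP calls exploratory.** True. It bears on the clarity of the safety report and leaves the primary analysis untouched.

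**Conclusion.** The gap is real and limited in scope. The only level specified for reactogenicity is arm by dose, and no specified output gives the share of patients reacting over six doses or their worst grade. For mild, moderate, any-grade and local reactions, by-dose rates leave that share undetermined: 10% to 60% of patients at an assumed 10% per dose, with 47% as the independence case and not the upper limit. The any-severe-systemic share is recoverable by summation, provided the stopping provision is followed.

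Later-dose rates are conditional on having been dosed. It would go too far to infer that a falling pattern will appear, or that it would be an artefact if it did. That depends on unequal risk between patients, on which the documents are silent. All rates used here are assumptions.

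**What to change.** In SAP 5.3.3.7 and Table 14.3.5.1:

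- Add an after-any-dose block by arm in the Safety Population: number and percentage of patients with each solicited event, any local event and any systemic event, each patient counted once at the worst grade over all doses.
- Keep the by-dose columns, show the number dosed in each, and label them as conditional on receiving that dose.
- Label the new block as added after the Week 24 analysis, since SAP section 2 already reports that result. The addendum's list of supplementary outputs does not include Table 14.3.5.1, so enter the revised table there.

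The cost is a few lines of SAP text and one descriptive block programmed from existing diary data. Nothing new is collected, and no dosing or stopping rule changes.

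### The grouped reactogenicity event totals in SAP 5.3.3.7 count symptom-days, so they and their split by grade mix frequency with duration

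*SAP*

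**What the plan says.** Protocol section 3.4 lists the safety endpoint as "Incidence and severity of local and systemic reactogenicity events". Duration is not part of it, although the next endpoint in the list, hepatitis flares, does include duration.

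SAP section 5.3.3.7 states the collection period: "Each patient will record local events, systemic events, and oral temperature in a diary daily for 7 days after each dose". It then plans two summaries.

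- **Patients.** "The number of patients with injection site reactogenicity events and each of the solicited events" is to be shown, with the same for systemic events. The section opens by saying "Incidence of reactogenicity events will be analyzed by treatment arm and dose number".
- **Events.** In addition, "number of events will be estimated for grouped injection site reactogenicity events", with a matching total for grouped systemic events. The counting rule follows: "Each event will be counted once by day of registration" in the diary card. The worked example reads: "if the same event is registered for 3 different days in the diary card of a specific dose, 3 events will be counted".

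Summaries are given overall and by mild, moderate and severe. The section does not say which day's grade applies when a symptom changes grade within the diary week. All diary entries are listed. The SAP's index of outputs has one reactogenicity table, 14.3.5.1, and its title describes the content as incidence.

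**The concern.** A reader who meets an event total in a table titled as incidence will take it as a number of reactions. Under the stated rule it is a number of symptom-days. If reactions to the adjuvanted vaccine last longer than reactions to saline, the ratio of event totals between arms will exceed the ratio of reactions, and the excess is duration.

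The split by grade has the same defect. Each day counts as a separate event, so a long reaction contributes more graded events than a short one, and the grade distribution is one of days rather than reactions. With no maximum-grade rule, a patient whose grade changes during the week could also appear under more than one grade in the patient counts.

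The SAP handles comparable data differently elsewhere. For hepatitis flares (sections 4.3 and 5.3.3.8) it defines an episode and reports incidence and duration separately. For treatment-emergent adverse events (section 5.3.3.2) it counts repeats once per patient and tabulates by maximum severity. Reactogenicity events are categorised separately from adverse events unless serious, so those rules do not carry over.

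What is at stake is how one descriptive tolerability table is read. No efficacy conclusion depends on it.

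**Working it through.** **Inputs from the documents.** Diary length 7 days per dose (SAP 5.3.3.7). Six doses (SAP 2.3.3). Four local and nine systemic solicited events (SAP 4.3 and 5.3.3.7).

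**Step 1: the SAP's own example.** Events for one symptom after one dose = number of distinct diary days on which it is recorded. Three days give 3 events, as the SAP states. Counted once per patient per dose, the same record gives 1.

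**Step 2: ceilings for one patient under the per-day rule.**

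| Total | Per-day rule | Once per dose |
|---|---|---|
| One symptom, one dose | 7 | 1 |
| Grouped local, one dose | 4 × 7 = 28 | 4 |
| Grouped systemic, one dose | 9 × 7 = 63 | 9 |
| One symptom, six doses | 7 × 6 = 42 | 6 |

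**Step 3: effect on a comparison between arms.** The inputs here are assumptions: 40 patients per arm, one symptom, one dose, and 50% of patients reacting in both arms, so 40 × 0.5 = 20 reacting patients per arm. Event total = reacting patients × mean days recorded.

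| Mean days, HepTcell v placebo | Patients | Event totals | Ratio of event totals |
|---|---|---|---|
| 1 v 1 | 20 v 20 | 20 v 20 | 1 |
| 2 v 1 | 20 v 20 | 40 v 20 | 2 |
| 3 v 1 | 20 v 20 | 60 v 20 | 3 |
| 7 v 1 | 20 v 20 | 140 v 20 | 7 |

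The patient counts do not move. With equal incidence, the ratio of event totals is simply the ratio of mean durations.

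**Step 4: effect on the grade split.** Two assumed patterns pull in opposite directions.

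- *Reaction that wanes.* Severe on day 1, moderate on day 2, mild on days 3 to 5. Per day: 1 severe event out of 5, or 20%. Per reaction at maximum grade: 1 of 1, or 100%.
- *Severe reaction that persists among brief mild ones.* One reaction severe on all 5 days, plus five mild reactions of 1 day each. Per day: 5/(5 + 5) = 50% severe. Per reaction: 1/6 = 17%.

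So per-day counting can lower or raise the severe share.

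**Step 5: evidence on duration in the documents.** Protocol section 1.3 reports, for the Phase 1 high-dose group with IC31, that reactions resolved by the next day in about half the subjects. Some reactions therefore lasted longer. That group received a higher peptide dose than this trial uses, so the statement shows that multi-day reactions are plausible but does not indicate their size here.

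**The case against.** The strongest reply is that the endpoint is already served. The same section reports the number of patients with any local event, any systemic event and each solicited event, with incidence analysed by arm and dose. A patient with a 7-day reaction counts once there. The per-day rule governs only an additional total for grouped events. This stands. A reader might infer that reactogenicity incidence as a whole is confounded with duration, and the documents do not support that.

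The rule is also disclosed with an example, every diary entry is listed (Listing 16.2.9.1), and section 5.3.3.7 specifies no test between arms. A careful reader can identify the unit and rebuild the reactions. This too stands, and it keeps the point small. It does not make the event total a count of reactions, nor does it supply the missing grade rule.

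A reader might further infer that the share of severe events is bound to be understated. That holds only if severe reactions have long milder tails; the second pattern in step 4 gives the opposite result. If the summaries by grade cover patient counts as well as event counts, as the text allows, a patient with one severe day would still appear under severe, whatever the later days show.

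**Conclusion.** The point holds for the grouped event totals and their split by grade. These totals are symptom-days, and the grade split weights reactions by how long they last, in a direction that cannot be fixed in advance. Patient-level incidence by arm and dose is sound; what it lacks is a stated maximum-grade rule for its split by severity.

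On size, 7 counts per symptom per dose is a ceiling, reached only if a reaction fills the whole diary. The threefold ratio rests on assumed mean durations of 3 days and 1 day with equal incidence. Neither should be read as the expected distortion, because the documents give no duration data for this dose in this population. If durations are similar in the two arms, the ratio of event totals is close to the ratio of reactions. This is a minor improvement to one descriptive safety table.

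**What to change.** In SAP section 5.3.3.7, replace the counting rule as follows.

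- Count each solicited event once per patient per dose, at the maximum grade recorded in that dose's 7-day diary. Apply this to the grouped event totals and to the patient counts by grade.
- Keep the per-day total if it is wanted, but report it separately, labelled as event-days and described as a measure of duration.

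For any one dose and arm, the revised grouped total will equal the sum of the patient counts over the symptoms in that group, which gives a simple programming check.

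The cost is reprogramming Table 14.3.5.1 from daily diary data already collected. The Week 24 outputs already exist, and the SAP addendum does not list this table among the supplementary outputs. The report should therefore state that the counting rule was changed after the interim analysis. Showing the table under both rules would make the effect of the change visible.
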